4 STUDY DESIGN

4.1 OVERALL DESIGN

This study will use a single-blind, parallel-arm RCT design. Participants will be randomized at a 1:1 ratio to Sleep GOALS intervention (n=20) or an education control group (n=20).

Sleep GOALS: We anticipate Sleep GOALS will be a 16-week intervention. However, the results of Aim 1 will determine the intervention length and core content. We will use a protocol [name] and colleagues developed to adapt TSC to an online format and integrate it with the GOALS lifestyle intervention.^{6,7} Briefly, in-person delivery of TSC has 3 components: 1) delivery of the core content, 2) providing tailored feedback, and 3) providing motivation and support. We will adapt the first component to an online format with 15-to-20-minute informational videos. The participants will view the material at their convenience, with new videos available weekly. The GOALS software will send weekly automated email reminders to review the new session materials. We will use a lifestyle coach to adapt the 2nd and 3rd components. Evaluating patient perspectives on the original GOALS lifestyle intervention found individualized lifestyle coaching, encouragement, and accountability helpful.⁸ The coach will be a master's level student in a health-related program (e.g., physical activity and health promotion, nutrition and dietetics, etc.) with experience in weight-management counseling. As described in Aim 1, the coach will assist with developing Sleep GOALS to familiarize them with the intervention content. However, the coach will complete a 2-day training workshop using a similar training format as the GOALS Lifestyle intervention.⁷ The coach will help participants develop an individualized sleep treatment plan based on their baseline sleep assessment. For example, coaches will encourage participants to document challenges for sleep (e.g., infant sleep, lack of partner support) and identify one treatment strategy they deem feasible to implement each week. The coach will monitor participant progress and engagement weekly to revise the sleep treatment plan, diet, and activity as needed. Coaches will provide personalized feedback and encourage accountability and re-engagement through a secure messaging system in the Sleep GOALS platform.⁷ The PI will randomly check coach-participant communication weekly to ensure intervention fidelity. IF NECESSARY, the PI will meet with the coaches weekly to discuss challenges and participant communication. Lastly, participants will be given a wireless scale for self-monitoring weight and a Fitbit for self-monitoring sleep (daily minutes) and physical activity (daily steps, minutes). The Fitbit dashboard also allows participants to track dietary calories. Participants will receive instructions on how to sync the scale and Fitbit data with the Sleep GOALS platform. Participants will be asked to weigh themselves in light clothing at least once weekly.⁹

Education Control: We used the Pragmatical Model for Comparator Selection in health-related behavioral trials to guide our control group selection.¹⁰ This model suggests utilizing a control group that is not likely to produce a change in the outcome for early-stage intervention development. We considered a no-treatment comparator and wait-list control. Given the timeline and limited resources, we decided a wait-list control is not feasible. We chose an education control because we decided the control should have some value to participants. Therefore, the control group will receive brochures from the American Academy of Sleep Medicine (e.g., sleep hygiene, sleep in women) and SNAP education connection (e.g., family-friendly activities, meal planning) after randomization is revealed.

4.2 SCIENTIFIC RATIONALE FOR STUDY DESIGN

Pilot testing will help us identify and refine factors related to the conduct of the planned larger, definitive trial and estimate the change in secondary outcomes. Given the timeline and limited resources, we decided a wait-list control is not feasible. We chose an education control because we decided the control should have some value to participants. Therefore, the control group will receive brochures with strategies to sleep better, eat healthily, be physically active, and lose weight.

4.3 JUSTIFICATION FOR DOSE

Over the 16-week intervention, participants will have access to 16 (~20-minute) information videos, made available weekly. The intervention content will be delivered via a secure online platform. Participants can access the intervention content at their convenience, which increases the intervention's feasibility for postpartum people with small children. The intervention 16-week are similar in dose to other weight loss interventions.

4.4 END OF STUDY DEFINITION

End of study is defined as completion of post-intervention assessments, which occur immediately following the 16-week intervention period (Week 16).

5 STUDY POPULATION

We will enroll 40 primiparous adult individuals between 3 \pm 1 and 6 \pm 1 months postpartum with a body mass index \geq 25 kg/m². We chose this postpartum range because postpartum weight retention during this period is associated with the development of long-term obesity. Additionally, at 3 months postpartum, most infants experience rapid increases in nocturnal sleep; thus, many of our behavioral strategies for improving maternal sleep may be more feasible. Evidence suggests that addressing sleep in infants between 3 and 6 months can prevent longer-lasting sleep problems. Lastly, it is safe for most postpartum individuals to participate in an intervention involving physical activity during this period.

5.1 INCLUSION CRITERIA

To be eligible to participate in this study, an individual must meet all of the following criteria:

1. Provision of signed and dated informed consent form,
2. Stated willingness to comply with all study procedures and availability for the duration of the study,
3. Primiparous, singleton pregnancy,
4. Between 3 \pm 1 and 6 \pm 1 months postpartum,
5. Has a body mass index $>$ 25 kg/m²,
6. Physically inactive, defined as self-reporting $<$ 150 minutes/week of moderate-to-vigorous intensity physical activity,
7. Endorse $>$ 1 indicator of poor sleep health based on the RU_SATED questionnaire, and
8. Has smartphone and home Internet access

5.2 EXCLUSION CRITERIA

An individual who meets any of the following criteria will be excluded from participation in this study:

1. current use of medications that affect weight (see Appendix 1),
2. currently pregnant or plan to become pregnant during the study period (18 weeks), and
3. participating in another weight loss intervention.

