1.2 SCHEMA

1.3 SCHEDULE OF ACTIVITIES (SOA)

Procedures	Screening, Day -7 to -1	Enrollment/Baseline, Day -7 to -1	Day 1	Final Assessment, Day 112+8
Eligibility determination	X			
Informed consent		X		
Randomization		X		
Administer the intervention			X-----X	
Outcome Assessment				
Feasibility indicators		X		
Acceptability indicators			X-----X	
Height and Weight	X	X		X
Descriptive characteristics				
Demographics	X	X		
Infant Feeding and Behavior		X		X
Mental Wellness		X		X

Treatment Expectations		X		
Weight Goals		X		
Social Support		X		X
Social Determinants of Health		X		
Health Behaviors				
Physical activity	X	X		X
Diet		X		X
Sleep	X	X		X

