2.3 RISK/BENEFIT ASSESSMENT

2.3.1 KNOWN POTENTIAL RISKS

We categorize the frequency of possible risk using the following categories: likely (occurs in >25% of people), common (occurs in 10-25% of people), infrequent (occurs in 1-10% of people), and rare (occurs in <1% of people). We will monitor the risk related to the intervention and data collection.

Intervention-Related Risk:

- The recommended physical activity may cause muscle soreness or fatigue (likely). There is the possibility that the following occurs during exercise: injury of a joint or muscle (common), broken bones (rare), falls from exercise equipment (infrequent). There is also the possibility of aggravating pre-existing problems (common), shortness of breath (common), abnormal blood pressure (common), fainting (rare), disorders of heart rhythm (rare), heart attack, stroke, or even death (rare).
- The recommended weight loss may cause constipation (common) and dizziness upon standing (common). Rapid weight loss increases the chances of developing or enlarging gallstones (rare). Other risks include hypoglycemia (infrequent), light-headedness or weakness (common), and hunger (likely).
- Wearing the wrist-worn activity monitor may cause some discomfort in the form of skin irritation (infrequent).

Data Collection Related Risk:

- The potential risks of participating in this study include discomfort (rare) from answering questions, disclosure of postpartum depression or child neglect/abuse (infrequent), and breach of confidentiality (rare).

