Appendix 1 – Medication exclusion list

Adipex-p
Aldosterone
Alli
Beclomethasone
Betamethasone
Buprenorphine
Carbamazepine
Carbatrol
Chlorpromazine Hydrochloride (CPZ)
Clozapine
Clozaril
Cortisol
Cortisone Acetate
Deixtcirtucisteribe Acetate (DOCA)
Depakote
Dexamethasone
Divalproex
Equetro
Eskalith CR
Eskalith
Fludrocortisone Acetate
Gabapentin
Haldol
Haloperidol
Hydrocortisone
Insulin
Lithium
Lithobid
Lomaria
Meridia
Methadone
Methylprednisolone
Neurontin
Naloxone
Naltrexone
Olanzapine
Orlistat
Phentermine
Prednisolone
Prednisone
Quetiapine
Risperidone
Risperdal
ReVia
Seroquel

Sibutramine
Suboxone
Subutex
Tegretol XR
Tegretol
Thorazine
Topamax
Topiramate
Triamcinolone
Valproic Acid
Vivitrol
Xenical
Zyprexa

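### No eligibility or screening item asks whether increased physical activity or weight loss is medically inadvisable for the person

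*Combined protocol and SAP*

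**What the plan says.** Section 5.2 excludes on three grounds. Two have some medical content: "current use of medications that affect weight (see Appendix 1") and "currently pregnant or plan to become pregnant during the study period (18 weeks"). The third is concurrent participation in another weight-loss intervention. Appendix 1, headed "Medication exclusion list", lists the drugs. Section 5.2 gives their effect on weight as the reason for excluding them.

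Section 5.1 has eight inclusion criteria: consent, willingness and availability, first birth with a singleton pregnancy, the postpartum window, a BMI floor, physical inactivity, poor sleep health, and smartphone and Internet access. The nearest to a suitability check is "Stated willingness to comply with all study procedures and availability for the duration of the study".

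In section 1.3 the screening column carries "Eligibility determination", height and weight, demographics, physical activity and sleep.

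On risk, section 2.3.1 states: "There is also the possibility of aggravating pre-existing problems (common), shortness of breath (common), abnormal blood pressure (common"). It also lists "heart attack, stroke, or even death (rare"). Common is defined there as 10-25% of people and rare as under 1%. Section 5 justifies the postpartum window partly on the ground that "it is safe for most postpartum individuals to participate in an intervention involving physical activity during this period".

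**The concern.** The protocol recognises that activity can worsen existing problems and that activity is not safe for everyone, but it has no step that identifies the people for whom it is not. Applying sections 5.1 and 5.2 exactly as written would admit a person whose clinician has advised against exercise or weight loss. The inactivity criterion may even favour such a person, because it does not ask why they are inactive.

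The Sleep GOALS programme is delivered online, with a coach working mainly by secure message and no in-person exercise supervision. According to section 4.2, the control brochures also cover being active and losing weight. At stake is avoidable harm to a participant who could have been identified with one question. The larger trial would also have no pilot experience of how many people such a criterion screens out.

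**Working it through.** There is no figure in the plan to reproduce. The check is a count of items, followed by a look for an equivalent safeguard elsewhere.

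**Eligibility criteria (5.1 and 5.2).** 8 inclusion + 3 exclusion = 11. Pregnancy and the drug list may remove some people at risk: 11 − 2 = 9 remain. Of those 9, 0 ask about a medical condition or clinician advice. There is no investigator-judgement exclusion.

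**Schedule of activities (1.3), headings not counted.** 4 procedural rows + 3 outcome rows + 7 descriptive rows + 3 health-behaviour rows = 17. Of these, 0 are a medical history or exercise-readiness item. Five rows are marked in the screening column, and none is a medical safety screen.

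**Assessments (8.1).** There are 8 bullets: anthropometry, demographics, mental wellness, infant sleep and eating, social determinants, social support, diet, and physical activity and sleep. Of these, 0 are a medical safety screen and none is tied to an eligibility decision. The PAQ is not expanded. It is listed with activity and sleep measurement, and no criterion refers to it.

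**Allocation (4.1).** 20/40 = 50% per arm. On average, half of any such people would receive the coached programme and half the brochures. This is the allocation ratio only and does not measure risk.

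**Other sections that might do the job:**

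| Safeguard | Section | Why it does not replace the question |
|---|---|---|
| Risks explained on the screening call and at consent | 5.4, 10.1.1.2 | Tells the participant about risks; no listed question about contraindications |
| Self-selected activities | 2.3.3 | Leaves the judgement to the participant |
| Weekly coach review; contact after two weeks without a login | 4.1, 6.3 | Comes after randomization, in the Sleep GOALS arm only; no medical history is collected to pass to the coach |
| Withdrawal for a medical condition | 7.2 | Discretionary and after enrolment |
| Withdrawal for an exclusion not recognised earlier | 7.2 | Adds no medical screen, since no exclusion names a contraindication |
| Adverse event inquiry | 8.2.4 | Detects events; does not screen people before exposure |

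None of these asks about a contraindication before randomization.

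**The case against.** The counts are not disputed. The case on the other side concerns weight.

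- **Small yield.** The question reaches only people who already know that activity or weight loss is inadvisable. They hear the risks twice and must state willingness to comply. The remedy, like the present arrangement, relies on self-report. This stands in part: the gain is modest and cannot be quantified. But a direct question is a firmer safeguard than waiting for someone to infer from a list of risks that they should decline.
- **The coach is not passive.** Weekly review covers diet and activity as well as the sleep plan, and re-engagement contacts ask about difficulties. A contraindication could therefore surface. That softens the gap, but the coach still depends on what the participant discloses, and only after allocation.
- **Control exposure is slight.** Section 4.1 describes leaflets on topics such as sleep hygiene, family-friendly activities and meal planning, with no coach or tracker. This stands: exposure is greater in the Sleep GOALS arm. Section 4.2 nevertheless says the brochures cover activity and weight loss, so the question is relevant to both arms.
- **The risk bands concern harm.** Calling aggravation of existing problems common does not show that contraindicated people are common. This is correct, and no such inference is made here.
- **Counting rows overstates the gap.** Many schedule rows could never carry such an item, so the three counts describe one absence and are not a magnitude. This is also fair.
- **Partial handling exists.** Appendix 1 removes users of insulin, corticosteroids and antipsychotics, for example, and the IRB approved the protocol. The pre-screen wording and the Manual of Procedures are not shown. Even so, sections 5.1 and 5.2 are the stated rules, and a person with a known contraindication who takes none of the listed drugs passes them.

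**Conclusion.** The concern holds. Apart from pregnancy and a drug list built around effects on weight, nothing in sections 1.3, 5.1, 5.2 or 8.1 identifies a person for whom more activity or weight loss is medically inadvisable. That person is eligible for either arm.

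The size in participants is unknown: the documents give no prevalence of contraindications, and none is assumed here. The argument rests on safety, not on attrition or precision. No primary endpoint is invalidated and no statement in the protocol is contradicted. It is a worthwhile, low-cost change that should be made. The conclusion assumes that the screening call and online pre-screen apply the criteria as written in sections 5.1 and 5.2.

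**What to change.** Add a fourth exclusion to section 5.2: a self-reported medical condition, or clinician advice, that makes increased physical activity or weight loss unsafe.

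Ask it as one question on the existing screening call, for example: *Has a clinician told you not to increase your physical activity or not to lose weight, or that you have a condition that makes either unsafe?* Confirm the answer at the baseline visit, before randomization. Self-report is enough; no clearance letter is needed. Report the number excluded on this ground alongside recruitment yield, so that the larger trial can plan for it.

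The cost is one protocol line and one question at two contacts that already take place, with no new procedure, instrument or staff. The downsides are a slightly lower screening yield and the conditions self-report will miss because the person is unaware of them.

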5.3 LIFESTYLE CONSIDERATIONS

This study does not have any lifestyle restrictions.

5.4 STRATEGIES FOR RECRUITMENT AND RETENTION

Recruitment Strategies

All subjects will be recruited from Allegheny County using participant registries maintained by Pitt's Institute for Clinical and Translation Research (i.e., Pitt+Me, Pediatric PittNet, Women's Practice-Based Research Network). The respective registries will identify participants through:

- Postings in practice waiting rooms
- Personalizing mailing and emails about the study to women that meet eligibility criteria based upon ICD-9/10 diagnosis codes listed in their medical record (e.g., recent delivery), demographics (e.g., women aged at least 18 years)
- Personalizing mailing and emails based on stated preferences (e.g., interest in weight loss interventions)

- A custom study web page that provides a lay description of the study, the eligibility criteria, compensation, and study team biographies
- Facilitating collaborations between study staff and practicing physicians, including practices that serve a diverse sample of women
- Advertisements on Facebook and Twitter

Interested participants will be pre-screened for eligibility online or through a registry call center. Referrals to contact potentially eligible subjects will be delivered through an online portal.

A research assistant will call women who agreed to be contacted to discuss the study purpose, procedures, risks, and benefits, screen for eligibility, and obtain verbal consent. Participants will be enrolled in the study once we obtain consent.

Retention Strategies:

The lifestyle coach will implement several strategies to increase engagement with the intervention protocol and re-engage participants who have not engaged with the online platform for two consecutive weeks. These strategies include:

- Personalized reminders: Send friendly messages through the GOALS platform to participants who haven't logged in for two weeks. Personalize the reminders by addressing the participant by name and mentioning specific content they have missed or need to catch up on.
- Motivational messages: Send motivational messages that highlight the benefits of the intervention and remind them of their goals and reasons for participating in the study.
- Check-in calls: Reach out to the participant by phone to check in on their progress, address any barriers, and offer support. This personal connection can help re-engage participants and reinforce the importance of their involvement in the study.
- Address technical issues: Some participants may be disengaged due to technical problems with the platform. Reach out to them to identify any issues they may be facing and provide assistance to resolve these problems.
- Reinforce incentives: Remind participants of any incentives associated with study participation, such as financial rewards, access to additional resources, or entry into prize drawings. This can help motivate them to re-engage with the platform.
- Monitor participant progress: Keep track of each participant's progress and send personalized feedback, praise, or encouragement based on their achievements. This can help maintain motivation and create a sense of accountability.
- Revisit participant goals: Encourage participants to re-evaluate their weight loss and lifestyle goals and discuss any necessary adjustments with their lifestyle coach. This can help maintain motivation and ensure the intervention remains relevant to the participant's needs.

6 STUDY INTERVENTION

6.1 STUDY INTERVENTION(S) ADMINISTRATION

6.1.1 STUDY INTERVENTION DESCRIPTION

Sleep GOALS is a 16-week online lifestyle intervention integrating content on sleep, diet, and physical activity, supported by coaching. For the purposes of this trial and registry reporting, intervention duration is defined as 16 weeks for all participants. The Sleep GOALS intervention will include the following components:

- 16 (~20 minutes) informational videos that provide strategies to improve sleep, diet, physical activity, and weight, delivered weekly through an online platform
- Lifestyle coach to provide personalized feedback, encouragement, motivation, and accountability
- A commercial activity tracker (e.g., Fitbit) to monitor sleep, diet, and physical activity
- Wireless scale to track weight

6.1.2 DOSING AND ADMINISTRATION

The participants will view the informational videos at their convenience, with new videos available weekly. The GOALS software will send participants weekly email reminders to review the new session material and to track relevant behaviors (e.g., physical activity, sleep).

6.2 MEASURES TO MINIMIZE BIAS: RANDOMIZATION AND BLINDING

We will use REDCap to generate the randomization plan. We will use blocked randomization (blocks of 4) to ensure balanced intervention groups. The randomization plan results will be maintained in REDCap and only accessible by a lifestyle coach who will support participants in the intervention arm (further detailed below) but is not directly involved with data collection. Assignment allocation will be concealed from participants until after the baseline assessments. Investigators will remain blinded until post-intervention data collection is complete.

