2.3.2 KNOWN POTENTIAL BENEFITS

Participants enrolled in both intervention arms of the study may benefit from losing weight and learning strategies to improve weight-related behaviors, i.e., dietary intake, physical activity, and sleep. Participants enrolled in the Sleep GOALS intervention arm may benefit from having a lifestyle coach who can provide them with tailored information to support behavior change. Society may benefit from the study information because it will inform an intervention to improve maternal weight and health postpartum.

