8.2.3.2 RELATIONSHIP TO STUDY INTERVENTION

All adverse events (AEs) must have their relationship to study intervention assessed by the PI, who examines and evaluates the participant based on temporal relationship and their judgment. The degree of certainty about causality will be graded using the categories below. In a clinical trial, the study product must always be suspect.

- **Related** – The AE is known to occur with the study intervention, there is a reasonable possibility that the study intervention caused the AE, or there is a temporal relationship between the study intervention and the event. Reasonable possibility means that there is evidence to suggest a causal relationship between the study intervention and the AE.
- **Not Related** – There is not a reasonable possibility that the administration of the study intervention caused the event, there is no temporal relationship between the study intervention and event onset, or an alternate etiology has been established.

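### Section 6.2 says investigators stay blinded, but Section 4.1 has the PI check coach messages that only one arm has, so the claim fails for the PI, and no one else is clearly protected

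*Combined protocol and SAP*

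**What the plan says.** Section 4.1 labels the trial: "This study will use a single-blind, parallel-arm RCT design". Section 6.2 conceals the assignment from participants until baseline assessments are done, and then says: "Investigators will remain blinded until post-intervention data collection is complete". After baseline, investigators are thus the only group that the protocol says stays blinded.

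Section 4.1 also gives the PI two tasks during the intervention. One is routine: "The PI will randomly check coach-participant communication weekly to ensure intervention fidelity". The other is conditional: "IF NECESSARY, the PI will meet with the coaches weekly to discuss challenges and participant communication".

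The coach belongs to one arm. Section 2.3.2 says: "Participants enrolled in the Sleep GOALS intervention arm may benefit from having a lifestyle coach". For the other arm, Section 4.1 says that "the control group will receive brochures from the American Academy of Sleep Medicine", together with other education material, and describes no coach or messaging.

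The PI has further duties. Under Section 8.2.3.2 all adverse events "must have their relationship to study intervention assessed by the PI". Section 7.1 lets the PI discontinue a participant whose eligibility changes. Section 10.1.2.1 puts data collection under the PI's supervision.

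On allocation, Section 6.2 says: "We will use blocked randomization (blocks of 4) to ensure balanced intervention groups". It restricts access to the randomization results to a lifestyle coach who is not directly involved in data collection.

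**The concern.** The two statements about the PI cannot both be carried out. A message between coach and participant exists only in the Sleep GOALS arm, so reading one reveals the arm of its sender.

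What is exposed is judgement. The relatedness of adverse events is the PI's decision, and so is discretionary discontinuation, which can bear on the primary retention benchmark of at most 20% loss to follow-up. The PI also directs the staff who measure weight. Weight change and postpartum weight retention are the secondary outcomes here, and Section 9.4.2 says they will be primary in the future trial. Section 8.1 assigns the measurements to a research team member without saying whether that person is blinded, so the only protection is the general sentence in Section 6.2.

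A further issue is concealment before assignment. It is promised only for participants, there is one block size and it is printed in the protocol, and nothing says that staff who enrol are kept from learning earlier assignments.

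**Working it through.** **The contradiction.** No arithmetic is needed.

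1. Section 6.2: investigators are blinded until post-intervention data collection ends, with no exception for the PI.
2. Section 4.1: the PI checks messages every week while participants are in the intervention, and may discuss participants with coaches.
3. Sections 2.3.2, 4.1 and 6.2: the coach serves the intervention arm only.
4. From 2 and 3, each participant whose messages are read or discussed is known to the PI as Sleep GOALS before the end point set in 1.

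**How many are exposed.** The documents give no sampling rate. Let q be the assumed chance that a given participant's messages are checked in a given week, independently over 16 weeks. The chance of being seen at least once is 1 − (1 − q)^16:

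- q = 0.05: 1 − 0.95^16 = 56%
- q = 0.10: 1 − 0.90^16 = 81%
- q = 0.25: 1 − 0.75^16 = 99%

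**Predictability, upper bound.** Inputs are the block size of 4 (Section 6.2) and the 1:1 ratio with N = 40, hence 10 blocks (Section 4.1). A 2:2 block has 6 equally likely orders. Suppose all earlier assignments and the block boundaries are known.

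- The third allocation is certain when the first two match, which happens in 2 of 6 orders. The fourth is always certain, in 6 of 6.
- Certain allocations per block: 2/6 + 6/6 = 8/6 = 1.33. As a share, 1.33/4 = 33%. Over 10 blocks, 13.3 of 40.
- Best-guess success by position is 1/2, 2/3, 2/3 and 1, averaging 2.833/4 = 70.8%, against 50% by chance.

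**Predictability, partial knowledge.** Let f be the assumed chance that an earlier intervention member of the block has been seen before the next enrolment. When f is below 1, an unseen person is not thereby known to be a control. An allocation is then certain only if both intervention members came earlier and both were seen. Both fall in the first two places in 1 of 6 orders and in the first three in 3 of 6. The share is (1/6 + 3/6) × f² / 4 = f²/6.

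| f | Certain | Best guess correct |
|---|---|---|
| 0 | 0% | 50% |
| 0.25 | 1.0% | 55.2% |
| 0.50 | 4.2% | 58.3% |
| 0.75 | 9.4% | 64.1% |
| 1 | 33.3% | 70.8% |

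The jump at f = 1 arises because unseen participants can then be inferred to be controls.

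**Timing.** The benchmark in Section 3 is 40 participants in 12 months. That is one every 52/40 = 1.3 weeks, so a block takes 5.2 weeks to fill. Weekly checks can therefore reveal members of a block that is still open.

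**Would varied blocks help?** With randomly mixed blocks of 2, 4 and 6 and all earlier assignments known, simulation gives about 4% certain allocations instead of 33%. Best-guess success is about 70.0% instead of 70.8%. Certainty mostly goes, but the guessing advantage stays. Setting f to 0 returns it to 50%.

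**The case against.** The strongest reply is that little follows from the contradiction. The trial is a descriptive pilot with no hypothesis test (Section 9.1), engagement is logged by the platform (Section 6.3), and weight is read from a calibrated digital scale (Section 8.1). This stands: it limits the likely bias, and none has been quantified for any outcome. It does not make the two sections compatible.

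A reader might go further than the documents allow in five ways.

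- **That blinding fails for everyone.** It is shown to fail only for the PI, and only for participants whose messages are read or discussed. Nothing says that the staff who measure outcomes see messages or assignments. Equally, nothing says that they are blinded.
- **That judging relatedness unblinds the PI.** The judgement covers all adverse events and reveals no arm. It is a task that knowledge of the arm can colour.
- **That the acceptability work unblinds the weight assessor.** Self-reported surveys are completed by link or QR code (Section 10.1.2.1), and the interviewer is not identified. The visit order is simply unstated.
- **That the PI enrols participants or supervises enrolment.** A research assistant screens (Section 5.4), consent is explained by an investigator not identified as the PI (Section 10.1.1.2), and the stated supervision concerns data collection.
- **That the coach can read the future list.** Section 6.2 gives the coach access to the results of the randomization plan and does not say whether unrevealed assignments are visible.

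**Conclusion.** The blinding statement is wrong as written for the PI. This follows from the text alone, without any assumption about sampling; the rate affects only how many participants are exposed. Two gaps go with it: no separate protection for the person measuring Week 16 weight, and concealment before assignment promised only for participants.

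That blocks of 4 make this trial's allocation predictable is not established. The 33% (about 13 of 40) is an upper bound that needs an enroller who knows every earlier assignment and the block boundaries, and the documents place nobody in that position. Under assumed partial knowledge (f from 0.25 to 0.75) it is about 1 to 9%.

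The effect on this pilot's estimates is probably modest. The correction is still worth making, because the pilot is meant to settle how the larger trial will be conducted.

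**What to change.** 1. Reconcile Sections 6.2 and 4.1. State that the PI and the coach are not blinded. Limit the blinding claim to the staff who measure outcomes and the analyst, and give them no access to the platform, the messages or the randomization table.
2. At Week 16, measure weight before any acceptability questionnaire or interview.
3. Set REDCap to release each assignment only after that participant's baseline, with future assignments hidden from everyone, the coach included.
4. State that staff who enrol are kept unaware of earlier assignments. This is what brings guessing back to chance.
5. Varying the block size is optional and secondary. It removes most certain allocations but barely lowers best-guess success, and it can leave a small imbalance such as 19 versus 21.

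The cost is protocol wording, visit order and a REDCap access setting. No extra staff are needed, provided that those who enrol and measure are already separate from the PI and the coach; the documents leave this open for the consenting investigator.
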